2.3. Benefit/risk assessment

No intervention will be administered in this study.

Detailed information about the known benefits and risks and expected AEs of RSV Maternal Vaccine (RSVPreF3) can be found in the IB.

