4.5.1. Adverse Events

Safety analyses in maternal participants will include summaries by study arms of MAEs, SAEs, SAEs due to study participation, and SAEs related to a GSK product.

Safety analyses in infant participants will include summaries by study arms and gestational age at birth (≥ 37 weeks; <37 weeks; overall) of MAEs, SAEs and SAEs due to study participation.

For MAEs until Day 42 post-delivery (Mothers: conception to Day 42 post-delivery; Infants: birth to Day 42), the number and percentage of maternal or infant participants with each MAE with exact 95% CIs will be tabulated by study arms and displayed by Medical Dictionary for Regulatory Activities (MedDRA) preferred term. By-participant listings will be prepared.

For SAEs and SAEs due to study participation, the number and percentage of participants with each SAE with exact 95% CIs will be tabulated by study arms and by MedDRA preferred term. By-participant listings will be prepared.

The number and percentage of maternal (or infant) participants and maternal pregnancies (based on pregnancies instead of subject) reporting

- at least one MAE
- at least one SAE
- at least one SAEs due to study participation

from study pregnancy conceived up to Day 42 post-delivery (or from delivery up to Day 42 post-delivery for infant participants) with exact 95% CIs will be tabulated by study arms.

A summary of number and percentage of participants with any recorded adverse events by maximum severity will be produced.

A separate summary will be provided for study intervention (administrated from previous RSV MAT studies) related MAEs and SAEs, respectively. A study intervention-related MAE (or SAE) is defined as a MAE (or SAE) for which the investigator classifies the possible relationship to study intervention from previous RSV MAT studies as “Yes”. A worst-case scenario approach will be taken to handle missing relatedness data, i.e. the summary table will include events with the relationship to study intervention as ‘Yes’ or missing.

Summaries of life-threatening and fatal SAEs by PT will also be created.

By participant listings of MAEs, SAEs and SAEs due to study participation will be prepared.

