6.2.2. Study Day and Reference Dates

The safety reference date is the conceived date of the study pregnancy and will be used to calculate study day for safety measures.

The study day is calculated as below:

- Assessment Date = Missing → Study Day = Missing
- Assessment Date < Reference Date → Study Day = Assessment Date – Ref Date
- Assessment Date ≥ Reference Date → Study Day = Assessment Date – Ref Date + 1

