6.2.3. Handling of Partial Dates

When partially completed dates (i.e. dates missing a day and/or month) are used in calculations, the following standard rules will be applied:

- A missing day will be replaced by 15
- A missing day and month will be replaced by June 30th.

The following exceptions apply.

| Element | Reporting Detail | | | | | | | | | | |
|---|---|-------------------|--|-----------------------------|--|-----------------|---|---------------------------|---------------|-----------------------------------|---------------|
| General | 
 Partial dates will be displayed as captured in participant listing displays. However, where necessary, display macros may impute dates as temporary variables for sorting data in listings only. In addition, partial dates may be imputed for 'slotting' data to study phases or for specific analysis purposes as outlined below. Imputed partial dates will not be used to derive study day, time to onset or duration (e.g., time to onset or duration of adverse events), or elapsed time variables (e.g., time since diagnosis). In addition, imputed dates are not used for deriving the last contact date in overall survival analysis dataset. | | | | | | | | | | |

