| Missing start day | 
If study intervention start date is missing (i.e. the conceived date of the study pregnancy), then set start date = 1st of month.
 
Else if study intervention start date is not missing:
 
 If month and year of start date = month and year of study intervention start date, then 
 If stop date contains a full date and stop date is earlier than study intervention start date, then set start date= 1st of month. Else set start date = study intervention start date. 
Else set start date = 1st of month.
 | | | | | | | | | | |
| Missing start day and month | 
If study intervention start date is missing (i.e. participant did not start study intervention), then set start date = January 1.
 
Else if study intervention start date is not missing:
 
 If year of start date = year of study intervention start date, then 
 If stop date contains a full date and stop date is earlier than study intervention start date, then set start date = January 1. Else set start date = study intervention start date. 
Else set start date = January 1.
 | | | | | | | | | | |
| Missing end day | A '28/29/30/31' will be used for the day (dependent on the month and year). | | | | | | | | | | |
| Missing end day and month | No Imputation | | | | | | | | | | |
| Completely missing start/end date | No imputation | | | | | | | | | | |

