6.2.4.8. Onset day

The onset day for an event (e.g. AE, concomitant medication/vaccination) is the number of days between the last prior study dose and the start date of the event. This is 1 for an event occurring on the same day as a prior study dose (and reported as starting after study dose).

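### SAP 6.2.3 defines its partial-date anchor inconsistently and has no date-of-birth anchor for infants, so some infant events with incomplete start dates are imputed to before birth

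*SAP*

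**What the plan says.** Protocol 2.3 states: "No intervention will be administered in this study". The partial-date rules in SAP 6.2.3 nevertheless depend on a *study intervention start date*.

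- In the adverse event rule for a missing start day, the term is explained as conception: "If study intervention start date is missing (i.e. the conceived date of the study pregnancy), then set start date = 1st of month". This agrees with SAP 6.2.2: "The safety reference date is the conceived date of the study pregnancy".
- In the rule for a missing start day and month, the explanation changes: "If study intervention start date is missing (i.e. participant did not start study intervention), then set start date = January 1". The concomitant-medication rows use this second explanation too.
- If the event month is not the anchor month, the missing-day rule ends with "Else set start date = 1st of month". The day-and-month rule for adverse events ends in the same way with 1 January.

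The adverse event rules cover all adverse events recorded in the CRF, for mothers and infants alike. No row mentions date of birth. SAP 4.5.1 summarises infant events over a window that starts at birth ("or from delivery up to Day 42 post-delivery for infant participants"). The General row of 6.2.3 says that "partial dates may be imputed for 'slotting' data to study phases". It also bars imputed dates from deriving study day, time to onset or duration.

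**The concern.** The rules look like template text for a trial with a first dose, only partly adapted to a study without one. For mothers, conception is a sensible anchor once it is stated in every row. For infants it does nothing useful. Conception lies months before birth, as does a prior vaccination, so the clause that would move an imputed date forward to the anchor never protects the birth date. The date falls to the 1st of the month or, for a year-only date, to 1 January or to the anchor itself.

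A rule that dates neonatal events before birth is wrong as written, in a study whose purpose includes neonatal safety. The errors concentrate in the first days of life. If a programmer uses imputed dates to decide which events belong in the birth-to-Day-42 summaries, the affected events could be misplaced.

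**Working it through.** The plan gives no figure to reproduce here, so the check applies the written rules directly.

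**Inputs.** From SAP 6.2.3: with a missing day, use the 1st of the event month unless that is the anchor month. With a missing day and month, use 1 January unless the event year is the anchor year, in which case use the anchor. From SAP 4.5.1: the infant window is birth to Day 42. Assumptions, not in the documents: births spread evenly over four calendar years (1,461 dates, 48 of them the 1st of a month); conception 266 days before birth; the onset distributions shown below. Day 0 is the day of birth.

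**One case.** An infant is born on 20 October and has an event recorded as October, day unknown. October is not the conception month, so the event is set to 1 October, 20 − 1 = 19 days before birth.

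**Missing day.** For onset k days after birth, the imputed date precedes birth when the event falls in the birth month and birth was not on the 1st. In a month of L days this holds for L − k − 1 birth dates. Every month has at least 28 days, so for k ≤ 27 the share is

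p(k) = 1 − 48(k + 1)/1461.

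- Day 0: 1 − 48/1461 = 96.7%
- Day 7: 1 − 384/1461 = 73.7%
- Day 14: 1 − 720/1461 = 50.7%
- Days 0-6 uniform (mean k + 1 = 4): 1 − 192/1461 = 86.9%
- Days 0-27 uniform (mean k + 1 = 14.5): 1 − 696/1461 = 52.4%
- Day 28: 72/1461 = 4.9%; Day 29: 28/1461 = 1.9%; Day 30 onward: 0%
- Days 0-42 uniform: [28 − 48 × 406/1461 + (72 + 28)/1461]/43 = 14.73/43 = 34.3%, where 406 is the sum of 1 to 28

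**Missing day and month.** The imputed date is not before birth only when the event falls in the calendar year after birth, or when birth was on 1 January. Over four years that is 4(k + 1) of the 1,461 birth dates, so the share before birth is 1 − 4(k + 1)/1461. For uniform Days 0-42 (mean k + 1 = 22) this is 1 − 88/1461 = 94.0%.

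| Assumed onset | Missing day: before birth | Year only: before birth |
|---|---|---|
| Day 0 | 96.7% | 99.7% |
| Uniform Days 0-6 | 86.9% | 98.9% |
| Uniform Days 0-27 | 52.4% | 96.0% |
| Uniform Days 0-42 | 34.3% | 94.0% |
| Uniform Days 28-42 | 0.5% | 90.1% |
| Exponential, mean 7 days | 75.8% | 98.0% |
| Exponential, mean 14 days | 60.6% | 96.6% |

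**Sensitivity.** Varying the conception-to-birth interval from 150 to 280 days left the Day 0 and Days 0-42 shares unchanged. Treating the anchor as missing gave the same shares in every row. The infant result therefore does not depend on how the inconsistent explanations are resolved.

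**Comparison.** The SAP's general default for a missing day (the 15th) would put 50.7% of Day 0 events and 9.7% of uniform Days 0-42 events before birth. The adverse event exception does worse than the rule it replaces. With date of birth as anchor and the same logic, the share is 0% in every scenario, for both rules.

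**The case against.** The strongest reply is that an odd imputed date need not change any count. The General row of 6.2.3 says only that imputed dates may be used for slotting, and it bars them from study day, time to onset and duration. No passage drops an infant event because of its imputed date. SAP 4.2.2 counts infants reporting an event at least once, with no date filter stated. Birth to Day 42 is also the collection window in the protocol's infant schedule. Several infant AESIs, such as preterm birth and low birth weight, are settled at birth whatever onset day is recorded. All of this stands, and it makes the consequence conditional. It does not rescue the rule, because the SAP never says whether imputed dates decide inclusion.

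Four stronger readings are tempting, and the documents do not support them.

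- *Infant events are lost or under-counted.* No text removes them, and the documents do not say how many dates are incomplete. The protocol's own warning of underestimation in the retrospective cohort (4.5) rests on recall bias.
- *Infant events with a missing day are usually dated before birth.* This holds only if onset clusters early. Over the full window with even onset the share is 34%.
- *The study has no such anchor, or maternal events are also dated before conception.* One row does equate the anchor with conception, in line with 6.2.2. Under that reading a year-only maternal event goes to conception or to a later 1 January. Dating it before conception requires reading the anchor as the earlier vaccination, which the rows do not state.
- *One event will carry two conflicting onset values because of imputation.* SAP 6.2.4.8 defines onset day as a count that "is the number of days between the last prior study dose and the start date of the event", whereas study day runs from conception. These are two differently named variables, and imputed dates do not feed study day or time to onset. The difference deserves a minor clarification, separate from this point.

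**Conclusion.** The concern holds as a defect in the stated rule. The anchor is explained in two ways, and infants have no anchor or floor at birth. The arithmetic assumes evenly spread birth dates and the onset patterns shown; the documents give no onset distribution. That an event in the birth month with a missing day is dated before birth, unless birth was on the 1st, follows from the rule without any onset assumption. The year-only rule is the worse of the two, at 90% or more in every scenario tried.

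The effect on results is possible but not demonstrated. It depends on whether imputed dates are used to assign events to the birth-to-Day-42 window and on how many infant start dates are incomplete; the documents settle neither. Because the rule yields impossible dates and is cheap to repair, it should be corrected before the final analysis.

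**What to change.** In SAP 6.2.3, replace the study intervention start date in every row with an anchor that is defined once:

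- maternal events and medications: the conception date of the pregnancy concerned;
- infant events and medications: the date of birth. A missing day in the birth month, or a missing day and month in the birth year, is set to the birth date unless the stop date shows otherwise.

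Add a sentence that an event recorded for an infant is not excluded from the birth-to-Day-42 analyses because of an imputed date. As a separate small clarification, explain how the reference dates in 6.2.2 and 6.2.4.8 relate to each other.

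The cost is SAP wording and minor programming. Date of birth is already collected (Protocol 8.1.1), so no new data are needed.

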6.2.4. Data derivation

6.2.4.1. Age in days

When age is to be displayed in days, it will be calculated as:

Age = date of event minus date of birth

6.2.4.2. Age in months

When age is to be displayed in months, it will be calculated as the number of complete calendar months between the date of birth (DOB) and the date of event. For example:

DOB = 10JUN2017, Date of event = 09JUL2018 -> Age = 12 months

DOB = 10JUN2017, Date of event = 10JUL2018 -> Age = 13 months

6.2.4.3. Age in years

When age is to be displayed in years, it will be calculated as the number of complete calendar years between the date of birth and the date of event. For example:

DOB = 10SEP1983, Date of first dose = 09SEP2018 -> Age = 34 years

DOB = 10SEP1983, Date of first dose = 10SEP2018 -> Age = 35 years

As day of birth is not collected for maternal participants, the day for DOB will be imputed as noted above, then age in years will be calculated.

6.2.4.4. Weight

Weight will be presented in kilograms. Weights reported in pounds will be converted as follows:

Weight in kilograms = Weight in pounds / 2.2

6.2.4.5. Height

Height will be presented in centimeters. Heights reported in feet and inches will be converted as follows:

Height in centimeters = Height in inches x 2.54

6.2.4.6. Body mass index (BMI)

BMI will be calculated as follows:

$BMI = (\text{Weight in kilograms}) / (\text{Height in meters})^2$

6.2.4.7. Temperature

Temperatures will be presented in degrees Celsius (°C). Temperatures reported in degrees Fahrenheit (°F) will be converted as follows:

$\text{Temperature (Celsius)} = ((\text{Temperature (Fahrenheit)} - 32) \times 5) / 9$

6.2.4.8. Onset day

The onset day for an event (e.g. AE, concomitant medication/vaccination) is the number of days between the last prior study dose and the start date of the event. This is 1 for an event occurring on the same day as a prior study dose (and reported as starting after study dose).

6.2.4.9. Duration of events

The duration of an event with a start and end date will be the difference between the start and end date plus one day, i.e. an event that starts on 03MAR2022 and ends on 12MAR2022 has a duration of 10 days.

The duration of solicited events will be calculated as the sum of the individual days with the adverse event reported at grade 1 or higher during the solicited event period.

6.2.4.10. Counting rules for combining solicited and unsolicited adverse events

All SAEs will be considered systemic events.

Multiple events with the same preferred term which start on the same day are counted as only one occurrence.

6.2.4.11. Counting rules for occurrences of solicited events

When the occurrences of solicited events are summarized, each event recorded as having occurred during a specific period will be counted as only one occurrence regardless of the number of days on which it occurs.

6.2.5. Display of decimals

6.2.5.1. Percentages

Percentages and their corresponding confidence limits will be displayed with one decimal except for 100% in which case no decimal will be displayed.

6.2.5.2. Differences in percentages

Differences in percentages and their corresponding confidence limits will be displayed with two decimals.

6.2.5.3. Relative risks

Two decimals will be displayed for all relative risk and their confidence intervals.

6.2.5.4. Demographic/baseline characteristics statistics

The mean, median, and SD for continuous baseline characteristics (height, weight, BMI) will be presented with one decimal.

The minimum and maximum values and quartile values (if required) will be presented with the same number of decimals as the observed values.

The minimum and maximum of transformed height variables will be displayed with no decimals.

The minimum and maximum of transformed weight variables will be displayed with no decimals with the exception of values are below 10kg where one decimal will be displayed.

The maximum and minima of transformed body temperatures will be displayed with one decimal.

6.3. Appendix 3 TFL for SRT safety monitoring

The Table Figure Listing (TFL) is planned for SRT safety monitoring. Other TFL may be provided if deemed necessary.

6.3.1. Listings

The planned listings include:

Demography and lifestyle characteristics – Maternal participants

Demography and lifestyle characteristics – Infant participants

General medical/vaccination history – Maternal participants

Vaccination administration from parent study

Listings of all AEs – Maternal participants

Listings of all AEs – Infant participants

Listings of medically attended AEs – Maternal participants

Listings of medically attended AEs – Infant participants

Listings of SAEs – Maternal participants

Listings of SAEs due to study participation – Maternal participants

Listings of SAEs – Infant participants

Listings of SAEs due to study participation – Infant participants

Listing of fatal AEs - Maternal participants

Listings of pregnancy outcomes

Listing of pregnancy related AEs of special interests during study pregnancy and up to 42 days post-delivery

Listing of neonatal AEs of special interest from birth up to 42 days post birth

6.3.2. Summary Table and Listing

| Table # | Table Title |
|-----------|---|
| Table 1 | Summary of demography and baseline characteristics - Maternal participants |
| Table 2 | Summary of demography and baseline characteristics - Infant participants |
| Table 3 | Number and percentage of infants with birth weight below the 3rd and 10th percentile, as per the IG-21 standards - Infant participants |
| Listing 4 | Listing of infants with birth weight below the 3rd and 10th percentile, as per the IG-21 standards - Infant participants |
| Table 5 | Number and percentage of infants with birth weight below the 3rd and 10th percentile, as per the IG-21 standards - Pre-term subgroup < 37 weeks - Infant participants |
| Listing 6 | Listing of infants with birth weight below the 3rd and 10th percentile, as per the IG-21 standards - Pre-term subgroup < 37 weeks - Infant participants |

| Table # | Table Title |
|----------------|---|
| Table 7 | Number and percentage of infants with birth head circumference below the 3rd and 10th percentile, as per the IG-21 standards - Infant participants |
| Listing 8 | Listing of infants with birth head circumference below the 3rd and 10th percentile, as per the IG-21 standards - Infant participants |
| Table 9 | Number and percentage of infants with birth head circumference below the 3rd and 10th percentile - Pre-term subgroup < 37 weeks, as per the IG-21 standards - Infant participants |
| Listing 10 | Listing of infants with birth head circumference below the 3rd and 10th percentile, as per the IG-21 standards - Pre-term subgroup < 37 weeks - Infant participants |
| Table 11 | Summary of study completion with reasons for withdrawal - Maternal participants |
| Table 12 | Summary of study completion with reasons for withdrawal - Infant participants |
| Table 13 | Summary of medically attended adverse events - Maternal subjects |
| Table 14 | Summary of SAE - Maternal subjects |
| Table 15 | Summary of AESI - Maternal subjects |
| Table 16 | Summary of medically attended adverse events - Infant subjects |
| Table 17 | Summary of non-medically attended adverse events - Infant subjects |
| Table 18 | Summary of SAE - Infant subjects |
| Table 19 | Summary of AESI - Infant subjects |
| Table 20 | Summary of participants with at least one grade 3 adverse event - Maternal participants |
| Table 21 | Summary of participants with at least one grade 3 adverse event - Maternal pregnancies |
| Table 22 | Summary of participants with at least one grade 3 related adverse event - Maternal participants |
| Table 23 | Summary of participants with at least one grade 3 related adverse event - Maternal pregnancies |

| Table # | Table Title |
|----------------|--|
| Table 24 | Summary of participants with at least one serious adverse event during study pregnancy and up to 42 days post-delivery - Maternal participants |
| Table 25 | Summary of participants with at least one serious adverse event during study pregnancy and up to 42 days post-delivery - Maternal pregnancies |
| Table 26 | Summary of participants with at least one serious adverse event from birth up to 42 days post birth - Infant participants |
| Table 27 | Summary of participants with at least one medically attended adverse event during study pregnancy and up to 42 days post-delivery - Maternal participants |
| Table 28 | Summary of participants with at least one medically attended adverse event during study pregnancy and up to 42 days post-delivery - Maternal pregnancies |
| Table 29 | Summary of participants with at least one medically attended adverse event from birth up to 42 days post birth – Infant participants |
| Table 30 | Pregnancy outcomes during study pregnancy and up to 42 days post-delivery - Maternal participants |
| Table 31 | Selected pregnancy outcomes during study pregnancy and up to 42 days post-delivery - Maternal participants from MAT-009 |
| Table 32 | Pregnancy outcomes during study pregnancy and up to 42 days post-delivery by age group - Maternal participants |
| Table 33 | Number and percentage of pregnancy related AEs of special interests during study pregnancy and up to 42 days post-delivery - Maternal participants |
| Table 34 | Number and percentage of participants reporting the occurrence of neonatal AEs of special interest from birth up to 42 days post birth – infant participants |
| Table 35 | Number and percentage of participants reporting the occurrence of neonatal AEs of special interest from birth up to 42 days post birth by gestational age at birth – infant participants |
| Table 36 | Summary of medical history - Maternal participants |

